6.5.2 Study Treatment Discontinuation Related to Postdose Cardiac Monitoring

A complete list of reasons for study treatment discontinuation is provided in [Section 7.1](#). All treatment discontinuations should be discussed with the Medical Monitor.

Reasons for study treatment discontinuation specific to postdose cardiac monitoring include the following:

- Participants who have a cardiovascular treatment-related symptomatic event (eg, chest pain, dizziness, palpitations, lightheadedness, shortness of breath, or syncope) associated with a clinically significant reduction of HR or associated with clinically relevant 12-lead ECG changes at any time during the 6-hour monitoring period on Day 1/OLE Day 1 or Day 2/OLE Day 2 (as applicable).
- Participants who have not met the discharge criteria on Day 1 (Week 0/Visit 2) or OLE Day 1 (OLE Week 0/OLE Visit 1) after ≥ 6 hours of extended monitoring and on Day 2/OLE Day 2 by 6 hours postdose (see [Section 6.5.1.2](#)).

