6.5.1.2 Extended Cardiac Monitoring

Participants who do not meet the discharge criteria at 6 hours postdose will require extended cardiac monitoring, as described below:

- Vital signs will be assessed hourly and 12-lead ECG may be performed, as clinically indicated, until the participant meets the discharge criteria ([Section 6.5.1.1](#)).
- Should a participant require pharmacologic intervention for symptomatic bradycardia, continuous overnight ECG monitoring in a medical facility should be instituted, and the first dose monitoring strategy should be repeated after the second dose of VTX002.
- Should postdose bradycardia (eg, HR < 50 bpm) or potentially related symptoms (eg, dizziness) occur, then initiate appropriate medical management, assess vital signs, begin continuous ECG monitoring, and continue observation until the symptoms have resolved.
- The Medical Monitor should be contacted if the participant does not meet the discharge criteria after ≥ 6 hours of extended cardiac monitoring.
- Any participant who requires extended monitoring on Day 1 (Week 0/Visit 2) or OLE Day 1 (OLE Week 0/OLE Visit 1) must return on the following day for the second dose and will be remonitored as on Day 1 (Week 0/Visit 2) or OLE Day 1 (OLE Week 0/OLE Visit 1), respectively. These participants will be discontinued from study treatment if they do not meet the discharge criteria at 6 hours after the second dose. Extended cardiac monitoring should be continued until the participant meets the discharge criteria ([Section 6.5.1.1](#)).

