 - If the ALC is confirmed to be below the 200 cells/ μ L limit, study treatment should be interrupted and should not be reinitiated if the ALC remains below this threshold. In this situation, the unblinded Medical Monitor will notify the Investigator and provide instructions on additional actions that the Investigator may need to take. When there is at least one measurement of ALC < 200 cells/ μ L, blinded values may be released to treating physicians and Investigators as deemed medically necessary to monitor infection and/or aid in diagnostic work-up as clinically indicated, and/or as a tool to assess the effectiveness of therapeutic interventions for an infection. Investigators will repeat CBC with differentials weekly until ALC > 500 cells/ μ L.
 - Reinitiation of study treatment can be considered only when ALC > 500 cells/ μ L.

A participant's study treatment must be discontinued permanently for any of the following reasons:

- Study participant is pregnant (see [Section 8.5.5](#))
- Decline in PFT values (FEV1 and/or FVC) below 50% of the predicted values
- Confirmed diagnosis of clinically significant macular edema, see [Section 8.4.6](#)
- Confirmed diagnosis of PML: Cases of PML have occurred in patients who have received S1P1 modulators. At the first sign or symptom suggestive of PML, withhold VTX002 and perform an appropriate diagnostic evaluation. The magnetic resonance imaging findings may be apparent before clinical signs or symptoms. Typical symptoms associated with PML are diverse, progress over days to weeks, and include progressive weakness on one side of the body or clumsiness of limbs, disturbance of vision, and changes in thinking, memory, and orientation leading to confusion and personality changes. The Investigator must notify the Medical Monitor of such symptoms.
- Cardiovascular events:
 - A participant experiencing a cardiovascular treatment-related symptomatic event (eg, chest pain, dizziness, palpitations, lightheadedness, shortness of breath, or syncope) associated with a clinically significant reduction of the HR or associated with clinically relevant 12-lead ECG changes at any time during the 6-hour monitoring period on Day 1 or Day 2 (as applicable) ([Section 8.4.3](#)). See also [Section 6.5](#) for cardiac monitoring during treatment initiation or reinitiation.

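### Protocol 6.5.1.2 sets a wider stopping rule after a failed Day 2 cardiac check than Protocol 6.5.2 and 7.1

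*Protocol*

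**What the plan says.** **Protocol 6.5.1.2 (Extended Cardiac Monitoring).** Entry to extended monitoring depends on one check: "Participants who do not meet the discharge criteria at 6 hours postdose will require extended cardiac monitoring". No minimum length of extension is set. Everyone extended on Day 1 or OLE Day 1 comes back the next day for the second dose and is monitored again. The stopping rule for them is: "These participants will be discontinued from study treatment if they do not meet the discharge criteria at 6 hours after the second dose". The 6-hour mark of the extension appears in this section only as a trigger for a call: "The Medical Monitor should be contacted if the participant does not meet the discharge criteria after" at least 6 hours of it.

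**Protocol 6.5.2 (Study Treatment Discontinuation Related to Postdose Cardiac Monitoring).** The matching item has two parts: failure on Day 1 or OLE Day 1 after at least 6 "hours of extended monitoring and on Day 2/OLE Day 2 by 6 hours postdose". It refers the reader to 6.5.1.2. The same section says: "A complete list of reasons for study treatment discontinuation is provided in" Section 7.1.

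**Protocol 7.1 (Discontinuation of Study Treatment).** The two-part item is repeated, again with a reference to 6.5.1.2, in the list whose lead-in is that "study treatment must be discontinued permanently for any of the following reasons".

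The SAP does not address the point.

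**The concern.** Section 6.5.1.2 makes the Day 2 result decisive for anyone who was extended on Day 1. Sections 6.5.2 and 7.1 add a Day 1 requirement that 6.5.1.2, the section they cite, does not contain. A site working from 6.5.1.2 and a site working from the 7.1 list could treat the same participant differently.

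This is a mandatory cardiac stopping rule for a drug whose first listed potential risk (Protocol 2.3) is reduced heart rate or AV conduction. It applies at Day 1 and at OLE Day 1, and first-dose monitoring is repeated when treatment restarts after an interruption (6.5.3). About 120 centers in 15 countries are planned, so differing interpretations are foreseeable.

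There is also a smaller consequence for the analysis. A participant stopped on Day 2 has had a dose and stays in the Full Analysis Set. If that participant's Week 13 outcome is then missing, SAP 16.1.2 counts it as non-response. The reading a site adopts can therefore affect an individual's efficacy status as well as exposure.

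**Working it through.** No arithmetic applies: no sample size, power, alpha or event count rests on this rule. The check sets the conditions side by side and goes through the possible outcomes.

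**The conditions**

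- 6.5.1.2: (extended on Day 1, for any length of time) and (fails at 6 hours after dose 2).
- 6.5.2 and 7.1: (still failing on Day 1 after at least 6 hours of extension) and (fails by 6 hours after dose 2).

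The Day 2 parts agree. The Day 1 parts do not.

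**Outcomes for a participant who fails the 6-hour check on Day 1**

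| Day 1 extension | Day 2 at 6 hours | 6.5.1.2 | Item in 6.5.2 and 7.1 |
|---|---|---|---|
| Still failing after at least 6 hours | Fails | Stop | Stop |
| Meets criteria before 6 hours (e.g. after 2 hours) | Fails | Stop | Not met |
| Either course | Passes | Not met | Not met |

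The rules part in the second row only. That row is a normal path through the protocol: 6.5.1.2 calls for hourly vital signs until the criteria are met, so extensions shorter than 6 hours are expected.

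**Can another reading remove the conflict?** The joining word in the 6.5.2 item could be taken to mark two separate triggers, one for Day 1 and one for Day 2. Failure on Day 1 after at least 6 hours of extension would then be enough to stop treatment. That contradicts 6.5.1.2, which brings those same participants back for a second dose and decides on the Day 2 result. Neither reading makes the sections agree.

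**A neighbouring gap.** The last item of 6.5.1.2 concerns participants discharged on Day 1 with continuing symptoms not linked to heart rate or ECG change. It also provides for stopping if symptoms occur on Day 2. Neither 6.5.2 nor 7.1 lists this as a specific item.

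**The case against.** The strongest reply is that this is an omission, not a pair of opposing instructions. Nothing in 6.5.2 or 7.1 permits a participant in the second row to continue, so a site that follows 6.5.1.2 breaches neither. Section 6.5.2 introduces its reasons as examples, and both narrower items refer back to 6.5.1.2. Section 7.1 also allows permanent discontinuation by Investigator decision, and 6.5.2 asks that all discontinuations be discussed with the Medical Monitor.

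These points reduce the conflict but do not remove it. Section 6.5.2 calls the 7.1 list complete, and that list carries the narrower item. Investigator decision is discretionary, whereas 6.5.1.2 is automatic. A site that reads 7.1 as not triggered has no discontinuation to discuss, and an extension shorter than 6 hours does not trigger the Day 1 call to the Medical Monitor either.

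Two parts of the objection stand:

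- **Reach.** It is narrow. A participant must fail on Day 1, recover in under 6 hours of extension, and fail again on Day 2. Doses on those days are 3 mg and 7 mg (Protocol Table 8), and in the Phase 1 single-dose cohorts heart rate was back to baseline by Hour 3 (2.2.2.5). These healthy-volunteer data suggest a small group but do not establish its size.
- **Permanence.** Only 7.1 says that stopping is permanent; 6.5.1.2 and 6.5.2 do not use the word. That is a further point to align.

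Inconsistent use across sites is therefore a foreseeable risk, not an established fact.

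**Conclusion.** The concern holds. Section 6.5.1.2 on one side, and 6.5.2 with 7.1 on the other, state different conditions for the same mandatory stop. They disagree for every participant whose Day 1 or OLE Day 1 extension ended with the criteria met in under 6 hours and who then fails at 6 hours on Day 2. The number cannot be derived from the documents. No planned statistical figure changes. The conclusion rests on the text alone and needs no assumption about how often the situation arises. The inconsistency should be corrected because the rule protects participants and should have only one reading. This review takes no view on which condition is clinically right.

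**What to change.** Reconcile Protocol 6.5.1.2, 6.5.2 and 7.1 so that the same condition, in the same words, appears in all three for both Day 1 and OLE Day 1. The sponsor's clinical team should choose the condition. In the same edit, state in each section whether the stop is permanent, and settle whether the Day 2 symptom item in 6.5.1.2 belongs in 6.5.2 and 7.1.

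For the main conflict the cost is wording in two places if 6.5.2 and 7.1 are changed, or in one place if 6.5.1.2 is changed; the two additions mean a few further words in the same sections. No design, sample size or SAP change follows.

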6.5.3 Cardiac Monitoring Upon Treatment Reinitiation Following Dose Interruption

Participants should undergo the same first-dose cardiac monitoring, as outlined in [Section 6.5.1](#), and dose titration, as outlined in [Section 6.2.1](#), procedures as the original treatment initiation when study treatment dosing is interrupted as follows:

- Missed treatment ≥ 2 consecutive days within the first week of treatment or
- Missed treatment ≥ 5 consecutive days after the first week of treatment

6.6 Guidance for Hepatic Monitoring

An increase in AST or ALT $> 3 \times$ ULN should be followed by repeat testing within 72 hours of receiving results to confirm the abnormality and determine whether AST or ALT is increasing or decreasing.

Discontinuation of study treatment for abnormal liver function should be considered by the Investigator when a participant meets one of the conditions outlined below or if the Investigator believes that it is in best interest of the participant. See also [Section 7.1](#) for more information.

- ALT or AST $> 8 \times$ ULN
- ALT or AST $> 5 \times$ ULN for > 2 weeks
- ALT or AST $> 3 \times$ ULN and total bilirubin $> 2 \times$ ULN or international normalized ratio (INR) > 1.5
- ALT or AST $> 3 \times$ ULN with the appearance of fatigue, nausea, vomiting, right upper quadrant pain or tenderness, fever, rash, and/or eosinophilia ($> 5\%$)

All events of ALT or AST $> 3 \times$ ULN and total bilirubin $> 2 \times$ ULN ($> 35\%$ direct bilirubin), or ALT or AST $> 3 \times$ ULN and INR > 1.5 , if INR measured, which may indicate severe liver injury (possible Hy's Law), must be reported as an SAE. See [Section 8.5](#) for follow-up and reporting of SAEs.

Because transient fluctuations of ALT or AST are common, and progression to severe drug-induced liver injury or acute liver failure is uncommon, automatic discontinuation of study treatment upon finding a greater than $3 \times$ ULN elevation of ALT or AST may be unnecessary.

6.7 Preparation/Handling/Storage/Accountability

The Investigator or designee must confirm appropriate temperature conditions have been maintained during transit for all study treatments received, and any discrepancies must be reported and resolved before use of the study treatment.

Only participants enrolled in the study may receive study treatment. The study treatment should be dispensed by the Investigator or by a qualified individual under the Investigator's supervision, according to the procedures described in this study protocol. All study treatments must be stored in a secure, environmentally controlled, and monitored (manual or automated) area in accordance with the labeled storage conditions with access limited to the Investigator and authorized study center staff.

The Investigator, institution, or the head of the medical institution (where applicable) is responsible for study treatment accountability, reconciliation, and record maintenance (ie, receipt, reconciliation, and final disposition records). The Study Monitor will ensure that all unused study treatment and all medication containers are returned or destroyed on site. Study treatment can be destroyed on site as long as proper documentation is available and permitted by local law.

Further guidance and information for the final disposition of unused study treatment and all the medication containers can be found in the Study Manual.

The Investigator, a designated member of the study center staff, or a hospital pharmacist must maintain an adequate record of the receipt and distribution of all study treatment using the Drug Accountability Form. These forms must be available for inspection at any time.

6.8 Measures to Minimize Bias: Randomization and Blinding

The study will employ a double-blind design for the Induction Treatment Period. Participants, Investigators, study center staff, persons performing the assessments, and the Sponsor are to remain blinded to the identity of the Induction Period treatment from the time of randomization until the interim database lock for the study.

All participants will be centrally assigned to randomized study treatment using an Interactive Web Response System (IWRS). Before the study is initiated, the log in information and directions for the IWRS will be provided to each study center. Participants will be randomized to a study treatment via stratified block randomization. The following will be used for stratification: (a) biologic/JAK inhibitor prior use status (Yes or No), (b) baseline corticosteroid use (Yes or No), and (c) baseline disease activity (MMS 5-6 or 7-9).

The study treatment and placebo tablets will be identical in physical appearance. There will be limited access to the randomization codes for the Induction Treatment Period. The treatment each participant will receive will not be disclosed to the Investigator, study center staff, participant, Sponsor, or study vendors (eg, central readers). The treatment codes will be held by the Clinical Supplies Department of the contract research organization (CRO). The IWRS will be programmed with blind-breaking instructions.

Investigators, study center staff, participants, and study vendors not engaged in data analysis associated with the interim database lock for the Induction Treatment Period will remain blinded to the identity of the LTE Period treatment. The Sponsor will be unblinded to study treatment for the LTE Period after the interim database lock and unblinding for the Induction Treatment Period.

Lymphocyte, neutrophils, [REDACTED] CRP, and FCP are considered markers for the mechanism of action for VTX002 or efficacy. For Investigators, study center staff, participants, and study vendors, total WBC, differentials, lymphocyte, neutrophils, [REDACTED] CRP, and FCP results will be blinded during the double-blind Induction Treatment Period, LTE Treatment Period, and the first 4 weeks of the OLE Treatment Period (see [Section 8.3.4](#)). These results will also be blinded to the Sponsor in the same manner until the interim database lock and unblinding for the Induction Treatment Period is completed. Then, the Sponsor will be unblinded to total WBC, differentials, lymphocyte, neutrophil, [REDACTED] CRP and FCP.

6.8.1 Emergency Unblinding Procedure

The participant's treatment group assignment blind will not be broken until the end of the study unless medical treatment of that participant depends upon knowing whether the participant is receiving active study treatment. In case of an emergency, the Investigator has the sole responsibility for determining if unblinding of a participant's treatment assignment is warranted. Participant safety must always be the first consideration in making such a determination. If the Investigator decides that unblinding is warranted, the Investigator should make every effort to contact the Medical Monitor or their designee prior to unblinding a participant's treatment assignment unless this can delay emergency treatment of the participant. If a participant's treatment assignment is unblinded, the Sponsor must be notified within 24 hours after breaking the blind. The date and reason that the blind was broken must be recorded in the source documentation and eCRF, as applicable.

6.9 Study Treatment Compliance

The prescribed dosage, timing, and mode of administration may not be changed, except as defined in [Section 6.4.2](#). Any departures from the assigned regimen must be recorded in the eCRFs.

Study treatment compliance will be measured by tablet count. At each visit, prior to dispensing the study treatment, the Investigator will retrieve the previously dispensed study treatment and assess compliance.

Overall, study noncompliance is defined as taking less than 80% or more than 120% of study treatment during the Induction Treatment Period and LTE Treatment Period. Participants will record tablet intake in the eDiary, which will be reviewed periodically by site staff and the Study Team. At each visit, the Investigator will collect the previously dispensed study treatment tablets and assess compliance. If there is a discrepancy between the compliance recorded in the eDiary and the tablet count, it should be discussed with the participant and noted in the source documents.

Participants exhibiting poor compliance should be counseled on the importance of good compliance to the study dosing regimen. Participants who are persistently noncompliant (< 80% or > 120%) should be discussed with the Medical Monitor to determine whether they should be withdrawn from the study.

Details of VTX002 study treatment administration will be documented in the eDiary. The participant will be provided with an eDiary to allow, at minimum, documentation of the date and time of the dose, date(s) of missed doses or partial dose administered while not in the clinic. This information will be transcribed into the participants' eCRF, as appropriate. Participants will be instructed to not take study drug prior to their clinic visits (except for the visits when study drug is not to be administered at the clinic), as predose samples will need to be collected prior to dose administration. While in the clinic, the date/time of doses administered in the clinic will be documented in the eCRF and eDiary. The time and date of study drug administration and the participant's most recent ingestion of food will also be recorded.

6.10 Prior and Concomitant Therapy

All concomitant medications, including over-the-counter or prescription medicines, blood products, vaccines, vitamins, holistic products, and radiotherapy, will be collected from Screening through the 2-Week Follow-Up visit and recorded in the eCRF. Any medication given for a study-related AE should be recorded from the time of informed consent.

The Medical Monitor should be contacted if there are any questions regarding concomitant or prior therapy. Medication history should be collected for at least 4 weeks prior to Screening.

6.10.1 Allowed Medications for the Treatment of Ulcerative Colitis

Oral 5-ASA, oral corticosteroids, or medicinal probiotics are allowed at the time of Screening; however, these products should not be started during Screening or during the treatment period in participants who are not already receiving them.

Immunosuppressive agents such as oral AZA or 6-MP must be discontinued > 2 weeks prior to Screening endoscopy.

Participants receiving 5-ASA or medicinal probiotics should maintain a stable dose throughout the Screening Period and study and can only be discontinued or reduced in dose if Investigator judgment requires it because of toxicity or medical necessity.

6.10.1.1 Corticosteroid Therapy

Oral corticosteroid therapy (prednisone at a stable dose of ≤ 20 mg/day, budesonide at a stable dose of ≤ 9 mg/day, or equivalent steroid) is allowed to be continued during the 13-week Induction Treatment Period provided the dose has been stable for the 2 weeks immediately prior to the Screening endoscopy assessment.

Participants entering the LTE Treatment Period will be tapered from corticosteroids. Participants entering the OLE Treatment Period may be tapered after 13 weeks of treatment in the OLE. The recommended tapering schedule for oral corticosteroids (other than budesonide extended release tablets [budesonide MMX]) is as follows:

- Dose > 10 mg/day prednisone or equivalent: taper daily dose by 5 mg/week until receiving 10 mg/day, and then continue tapering by 2.5 mg/week until 0 mg/day
- Dose ≤ 10 mg/day prednisone or equivalent: taper daily dose by 2.5 mg/week until 0 mg/day

The recommended tapering schedule for participants receiving oral budesonide MMX 9 mg/day is to reduce tablets to 9 mg two days out of three for 2 weeks, followed by 9 mg one day out of three for 2 weeks, and then discontinue.

For participants who cannot tolerate the corticosteroid taper without recurrence of clinical symptoms of either UC or steroid withdrawal, the corticosteroid dose may be increased (up to the dose at study entry if required), but tapering should be attempted again within 2 weeks.

